### 9.2.1 Treatment Assignment Procedures

At the time of MBDC enrollment (registration on the Presence Care site), a CP will be presented with several currently enrolling class options (multiple days/times of week) and asked to select two that work with their schedule. Approximately 4 weeks prior to the course start date, they will then be randomly enrolled in one of the two selected courses, allowing for randomization on the class level while still accommodating the participant's schedule. An adaptive randomization schematic will be used to adjust the probability of class assignment based on CPs already enrolled in the trial. Since randomization is preferred in the full-scale ePCT, it is important to assess the feasibility of the acceptability of the random assignment in this pilot. Once a CP has registered for a MBDC course, there is variable delay period until there are enough people to fill the class. During this time, Presence Care will send regular emails updates to stay in contact. Once a class option is full, CPs will be notified, and the class will start. If a CP situation or schedule has changed and they decline the assigned course, they will have the option choose a preferred day and time so that we do not deny anyone access to this program.

## 9.3 Interim analyses and Stopping Rules

No interim analysis is planned as this is a one-year pilot study. There are no statistical rules that would suspend MBDC program enrollment. The Safety Officer and NIA may decide to stop this study based upon review of data provided by the statistician.

## 9.4 Outcomes

### 9.4.1 Primary outcome

To assess the feasibility, acceptability, and fidelity of implementation of the MBDC program, primary outcomes will include: number of CP participants contacted for recruitment, number of CP enrolled, missingness in the class registration materials, response rate to the four questionnaires, completeness of the administrative generated data, CP attendance and module completion rates.

### 9.4.2 Secondary outcomes

To determine the feasibility of obtaining clinical outcome measures, secondary outcomes will include response rates and completeness of data for CED-D-10 and ZBI-6. To explore the feasibility of obtaining online consent for research access to CP

healthcare utilization records, exploratory outcomes will include the number of CPs who agree and consent to research access included on Questionnaire 3.

## 9.5 Data Analyses

**Aim 1- Primary Feasibly Analysis:** To assess the feasibility, acceptability, and fidelity of implementation of the MBDC program we will beginning by measuring the absolute number of potential CPs contacted for recruitment and the number of those who complete the online course enrollment. The total number of mailed flyers will be counted. Adding documentation of flyer distribution to the current clinic workflow is too large of a barrier for this pragmatic trial. An estimate of flyers distributed in the clinics will made by asking clinic directors for total numbers of flyers printed. These will be used to calculate the overall rate of program registration as well as broken down by referral site. The feasibility of collecting patient provided data will be evaluated by quantifying the missingness in the class registration materials as well the response rate to the four questionnaires. The completeness of the administrative generated data, including date of enrollment, course section, and attendance, will also be quantified. Fidelity of the intervention will be assessed by describing CP attendance and module completion rates as recorded by Presence Care staff. Completion patterns will be summarized overall and stratified by patient demographics and study site. The fidelity of the make-up video module offerings as a substitute for in-class participation will be evaluated by comparing course outcomes between CPs who completed the course fully in-class and those who utilized the make-up modules. Any differences in intervention fidelity associated with CP demographics will be described and discussed. Table 3 gives an example of how counts will be utilized to describe the recruitment, enrollment, and adherence. The 3-month post-intervention questionnaire will be sent to all CP participants and the response rate and patterns for CP with adequate follow-up time within the study timeframe will be described. We expect that 60% of participants will have at least 3-months to reply to these additional questionnaires before the final analytic data is aggregated.

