**Table 1. MBDC Session Topics**

CLASS	TOPIC
1	Introduction to Mindfulness-Based Dementia Care -and one another!
2	Attitudinal Foundations & Beginning Practice
3	Living Grief & Self-Compassion
4	Coming to Our Senses
5	Everyday Communication
6	Being with Difficulty
7	(Retreat)
8	Deepening Practice -Day of Mindfulness
9	Caring for Yourself
	Reflecting Backward & Practicing Forward

transfer of data from healthcare settings to Presence Care. All questionnaires will include the same items, with an addendum added to the third questionnaire, which will include course evaluation and a theoretical assessment of willingness to share healthcare utilization data. Our Aim 3 goal is to determine whether CPs will be willing to consent online to share their insurance information evaluate healthcare utilization in future studies. The question would be “In the future, we wish to study how the MBDC affects health care utilization. If we were to do so, would you be willing to provide your Medicare ID number to help us understand how this program affects your health? Please note that we are not asking you to provide this information now, nor are collecting your utilization data.” A second question will ask if they are a legally authorized individual for the PLWD, and if so, would they theoretically consent to also sharing the Medicare ID of that individual. We will not collect the Medicare ID number but ask theoretically if they would consider participating and offer the choices of “yes/no/I don’t know”.

**Table 2.** Data elements collected. All items will be a permanent part of Presence Care administrative data collection.

Data Forms	Time Point Collected	Entered By	Detailed Data Elements
Class Registration	Initial Registration	CP	Name, Address, Date of Birth, Phone Number, Referral Source, Race, Ethnicity, Language, Education, Length of Caregiving, Relationship to PLWD, Preferred Classes, Emergency Contact
		CP (about PLWD)	Name, Type of Residence, Date of Birth, Dementia Diagnosis
Questionnaire 1,2, 3, 4	Initial Registration (Q1), Week before MBDC (Q2), Week after MBDC (Q3), 3 months after MBDC completion (Q4)	CP	Clinical Outcome Scales: Depressive Symptoms (CES-D-10  ) and Caregiver Burden (6-item Zarit Burden Interview, ZBI-6  )
			CP Behavior Change Measures (: Self-Compassion (The State Self-Compassion Scale Short Form, SSCS-S)  and Mindfulness (The 5-Item Mindful Attention Awareness Scale – State)  )

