### **4.3 Study Enrollment Procedures**

**Recruitment:** Each pilot site has an established Presence Care certified instructor with 3-7 years of experience teaching MBDC to CPs referred by the memory clinic in their health system. In preparation for a future larger study, we will train one new MBDC instructor as part of this pilot. MBDC courses are ongoing, with systems in place at each site for referring CPs, and classes being held virtually due to the COVID-19 pandemic. Participants will be referred from memory care clinics at each of the three aligned healthcare settings using flyers. Flyers are handed out by clinicians (physicians, advance-practice providers, neuropsychologists) during clinic visits to those CPs they feel would benefit from the program. Referrals using flyers at clinics may also occur during conversations with non-clinician staff (social work, Care Ecosystem). Flyers are posted on the clinic website and public spaces in the clinic. Partnerships with community-based programs surrounding the pilot sites are also in place including sharing MBDC flyers with local day programs and the Alzheimer's Association. Interested CPs referred to the MBDC program will visit the Presence Care website to register using the centralized system.

In addition to the current practices above, this pilot will use additional strategies to maximize the participation of diverse CPs in our communities. In addition, at HealthPartners, we will request a waiver of consent to identify PLWD through the electronic health record and healthcare claims data, and mail letters with MBDC flyers to families with over-sampling of non-white and Hispanic patients. The study team programmer will identify patients using ICD-10 diagnostic codes for dementia or mild cognitive impairment (F00-F03, G30-G31.9) documented at least two outpatient or inpatient encounters or if present on to the problem list (a list of diagnoses on a patient's electronic health record dashboard) in the electronic health record. At HealthPartners, patients can opt out of use of their data for research. We will exclude patients from mailings who have declined permission for their medical records to be used in research. CPs interested in participating will be directed to visit the Presence Care website to register using the centralized system.

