**Table 3.**

	Counts for feasibility	Use in analysis
Participants contacted	N	Total number of targeted mailings Estimate of clinic flyer distribution using print rates
Participants who enroll and are randomized into MBDC course section	a	Recruitment rate: a/N
Participants who start MBDC course	b	Participation rate: b/N, compare to a/N
Participants who complete course (6/9 modules)	c	Completion rate: c/b, used as main progression criteria Overall successful enrollment rate: c/N
Number who complete each module in real-time – k = 1, ..., 9	d k	Module specific completion rate: d k /b

Number who complete each module as a make-up session – k = 1, ..., 9	$e_k$	Module specific make-up completion rate: $e_k/b$ Compare to $d_k/b$ to assess fidelity of make-up offerings
Number who complete each questionnaire – m = 1,2,3	$f_m$	Questionnaire specific response rate: $f_m/a$ and/or $f_m/b$ if $a \neq b$

**Aim 2 - Secondary Feasibility and Efficacy Analyses:** The completeness of the CED-D-10 and ZBI-6 outcomes will be quantified by calculating the rate of CPs that respond to all items on each scale (CES-D-10: 10 items, ZBI-6: 6 items) at each assessment. The rate of completion for both scales will be presented overall and stratified by questionnaire, site, and by CP demographics. As the current study design results in a non-uniform length of the control period, the weeks between Q1 and Q2 will be recorded and summarized for the sample to better understand how the design could scale to a larger ePCT. A preliminary efficacy analysis will utilize the total scores for the CES-D-10 (range: 0 to 30) and ZBI-6 (range: 0 to 24) calculated for all completed questionnaires. Both outcomes will be summarized at each questionnaire timepoint using means and/or medians, as appropriate. Change over the control (Q2-Q1) and intervention (Q3-Q2) periods will be calculated for each CP and summarized for the sample. Descriptive summaries will be provided for responses from CP who complete the 3-month follow-up questionnaire (Q4) within the 12-month study timeframe and before the final analytic dataset is defined. These responses will not be used in any of the formal inferential analyses.

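### The Table 3 rates a/N, b/N and c/N count care partners from every recruitment channel, but N covers only mailed letters and printed clinic flyers, so they are not proportions of people contacted

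*Combined protocol and SAP*

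**What the plan says.** Table 3 (Section 9.5) lays out the recruitment counts. N is labelled as participants contacted, and its content is given as "Total number of targeted mailings Estimate of clinic flyer distribution using print rates". The count a is "Participants who enroll and are randomized into MBDC course section", with no condition on how the person was reached. The summary is "Recruitment rate: a/N". Starters (b) and completers (c) are also divided by N.

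The Aim 1 text explains where N comes from. For letters, "The total number of mailed flyers will be counted". For clinics, "An estimate of flyers distributed in the clinics will made by asking clinic directors for total numbers of flyers printed", because logging each handout is judged too burdensome for a pragmatic trial. The text commits to an overall registration rate and a breakdown by referral site. It describes the enrolled as a subset of the CPs contacted.

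Other sections describe more routes into the program. Section 4.3 states: "Flyers are posted on the clinic website and public spaces in the clinic". It also describes community partnerships, including "sharing MBDC flyers with local day programs" and the Alzheimer's Association. Section 3 names community partners as a referral source, and Section 11.2 says that clinic newsletters and/or notices carry information about the program. The class registration form in Section 3, Table 2 collects "Phone Number, Referral Source, Race, Ethnicity, Language, Education", so each registrant is asked how they were referred.

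**The concern.** A recruitment rate can be read as a proportion only if everyone in the numerator could also be counted in the denominator. Here a CP who found the program on the clinic website adds one to a and nothing to N. A printed flyer that nobody took adds one to N and reaches no one. A family that received both a letter and a flyer counts twice in N.

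What is at stake is interpretation. Section 9.4.1 lists the number contacted and the number enrolled as primary feasibility outcomes, and a/N is their planned summary. Section 4.3 adds the HealthPartners mailing, with over-sampling of non-white and Hispanic patients, to widen participation. Section 9.1 says recruitment strategy will be revisited if enrollees are not representative. A pooled a/N cannot show how well the mailing, or any other channel, performed.

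**Working it through.** **Step 1. Compare each channel with the two counts.**

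| Channel (source) | Can enter a? | Counted in N? |
|---|---|---|
| HealthPartners letters (4.3, 9.5) | Yes | Yes, exact count |
| Flyers handed out in clinic (4.3, 9.5) | Yes | Yes, through the print total |
| Flyers posted in clinic spaces (4.3) | Yes | Probably as sheets printed; readers are not counted |
| Flyers at community partners (3, 4.3) | Yes | Not named; depends on whether clinics print them, which is not stated |
| Clinic website (4.3) | Yes | No |
| Clinic newsletters (11.2) | Yes | No |

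The last two rows are clearly outside N. The community row may be.

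**Step 2. Look for a figure to reproduce.** There is none. The documents give no number for letters, flyers printed, N, a/N or enrollees by channel.

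**Step 3. Write down the error.** Let M be letters mailed, P flyers printed, s the share of enrollees from channels outside N, and q the share of printed flyers handed out.

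- Planned rate = a/(M + P)
- Channel-matched rate = a(1 − s)/(M + qP)
- Planned ÷ matched = (M + qP)/[(M + P)(1 − s)]

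The count a cancels from the ratio. With q = 1 the ratio is 1/(1 − s), whatever M and P are.

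**Step 4. Illustrate.** a = 130 is the enrollment ceiling in Section 9.2. M, P, s and q are assumptions.

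| M | P | s | q | Planned | Matched | Ratio |
|---|---|---|---|---|---|---|
| 1000 | 500 | 10% | 1 | 130/1500 = 8.7% | 117/1500 = 7.8% | 1.11 |
| 1000 | 500 | 25% | 1 | 8.7% | 97.5/1500 = 6.5% | 1.33 |
| 1000 | 500 | 40% | 1 | 8.7% | 78/1500 = 5.2% | 1.67 |
| 1000 | 500 | 0 | 0.5 | 8.7% | 130/1250 = 10.4% | 0.83 |
| 500 | 1000 | 0 | 0.5 | 8.7% | 130/1000 = 13.0% | 0.67 |
| 1000 | 1000 | 25% | 0.5 | 130/2000 = 6.5% | 97.5/1500 = 6.5% | 1.00 |

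Enrollees from outside N push a/N up, and unused flyers push it down. The last row shows that the two can cancel. Families reached twice are not modelled; removing duplicates would lower the denominator further.

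**Step 5. See what does not depend on N.** The completion rate c/b contains no N. The planned comparison of b/N with a/N reduces to b/a, because N cancels.

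**Step 6. Check whether the by-site breakdown repairs the mismatch.** Section 4.3 describes the records-based mailing at HealthPartners only. There, N would still mix letters with flyers. At the other two sites it would be flyers alone, so the site rates would differ in what they measure. The plan does not say to which site a community registrant is assigned.

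**The case against.** The strongest reply is that this is a crude descriptive rate with no decision attached, and that its main weakness is disclosed. Much of that stands.

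- A reader might infer that a primary endpoint or a go/no-go rule is compromised. The documents do not support this. Section 9.4.1 lists counts, not a/N. The progression criteria in Section 9.1 are attendance at 6 of 9 sessions and representativeness, and Table 3 names c/b as the main criterion.
- A reader might infer that a/N will fix the outreach volume of the full trial. No section says so. Section 9.2 names power calculations, specifically the ICC, as the use of the pilot results.
- The plan says that the clinic count is an estimate and why, and it introduces Table 3 as an example of how counts will be used.
- Posted flyers, and perhaps community flyers, may lie inside the print total. It would be too strong to say that every channel other than mail and handouts is missing from N.
- The by-site breakdown probably draws on the referral source field, so that field may not be wholly unused.

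What the reply does not reach is the numerator. The disclosed limit concerns how flyers are counted. It does not acknowledge that enrollees may come from channels that N never covers. The by-site split does not separate channels at the one site with mailings. The burden argument does not apply either, since the correction needs no flyer log.

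**Conclusion.** The point holds as a defect of definition and labelling in descriptive rates. As written, a/N, b/N and c/N are not proportions of participants contacted. Website and newsletter arrivals are outside N, and community arrivals may be.

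The size cannot be established from the documents. The ratios of 1.11 to 1.67 assume that 10% to 40% of enrollees come from outside N and that every printed flyer is handed out. The ratios of 0.67 to 0.83 assume no such enrollees, half the flyers unused, and the letter-to-flyer mixes shown. It would be tempting to conclude that the recruitment rate is overstated. That does not follow, because the net error could have either sign or be nil.

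The progression criterion c/b is untouched. The change is still worth making because the data for a matched rate are already planned.

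**What to change.** 1. In Table 3, relabel N as approximate outreach items (letters mailed plus flyers printed). Describe a/N, and b/N and c/N if kept, as crude outreach yields.
2. Tabulate enrolled and randomized CPs by referral source, with a row for missing or multiple sources.
3. For HealthPartners, report mail-referred enrollees divided by letters mailed as a channel-matched response rate.
4. Show clinic-flyer enrollees against flyers printed, marked as approximate, with the print total stated to be an upper bound on distribution.
5. Report website, newsletter and community sources as counts only.

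The cost is a wording change in Table 3 and one cross-tabulation. No new data are needed if the referral source field distinguishes these channels; its response options are not given and should be checked before registration opens.

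There are two limits. Self-reported source can be missing, since Section 11.2 lets registrants skip items, and it is ambiguous when a family saw both letter and flyer. The mail rate describes one site's over-sampled mailing, with letters addressed to patients (Section 11.3). It should stand beside the overall yield and must not be presented as the study-wide recruitment rate.

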**Table 3.**

	Counts for feasibility	Use in analysis
Participants contacted	N	Total number of targeted mailings Estimate of clinic flyer distribution using print rates
Participants who enroll and are randomized into MBDC course section	a	Recruitment rate: a/N
Participants who start MBDC course	b	Participation rate: b/N, compare to a/N
Participants who complete course (6/9 modules)	c	Completion rate: c/b, used as main progression criteria Overall successful enrollment rate: c/N
Number who complete each module in real-time – k = 1, ..., 9	d k	Module specific completion rate: d k /b

Number who complete each module as a make-up session – k = 1, ..., 9	$e_k$	Module specific make-up completion rate: $e_k/b$ Compare to $d_k/b$ to assess fidelity of make-up offerings
Number who complete each questionnaire – m = 1,2,3	$f_m$	Questionnaire specific response rate: $f_m/a$ and/or $f_m/b$ if $a \neq b$

**Aim 2 - Secondary Feasibility and Efficacy Analyses:** The completeness of the CED-D-10 and ZBI-6 outcomes will be quantified by calculating the rate of CPs that respond to all items on each scale (CES-D-10: 10 items, ZBI-6: 6 items) at each assessment. The rate of completion for both scales will be presented overall and stratified by questionnaire, site, and by CP demographics. As the current study design results in a non-uniform length of the control period, the weeks between Q1 and Q2 will be recorded and summarized for the sample to better understand how the design could scale to a larger ePCT. A preliminary efficacy analysis will utilize the total scores for the CES-D-10 (range: 0 to 30) and ZBI-6 (range: 0 to 24) calculated for all completed questionnaires. Both outcomes will be summarized at each questionnaire timepoint using means and/or medians, as appropriate. Change over the control (Q2-Q1) and intervention (Q3-Q2) periods will be calculated for each CP and summarized for the sample. Descriptive summaries will be provided for responses from CP who complete the 3-month follow-up questionnaire (Q4) within the 12-month study timeframe and before the final analytic dataset is defined. These responses will not be used in any of the formal inferential analyses.

Analysis will utilize linear mixed-models with random effects to account for clustering of data within MBDC course section as well as repeated measures within CPs to estimate the intervention effect on depressive symptoms and care-giver burden (Equation 1). In a scaled up ePCT, we expect the unit of randomization to continue to be course section, which is reflected in our choice of random effects. The model structure will be based on a standard ANCOVA used to evaluate change that adjusts for the pre-intervention measurement of the outcome variable with the post-intervention measurement as the model outcome. Each CP will contribute a pair of data points for the control period (Pre: Q1, Post: Q2) and intervention period (Pre: Q2, Post: Q3) which requires our random effects structure to account for repeated measurements within CPs. If there is no difference in change in efficacy outcomes, we expect Q2-Q1 = Q3-Q2. Each model will include covariates to adjust for possible confounding associated with CP demographics and CP history (age, race/ethnicity, socioeconomic measures, and length of caregiving). While the relative time of measurement is considered (pre/post) our analysis does not adjust for time over the course of the study, as we hypothesize any treatment effect would be time-agnostic within the year-long pilot study time frame. When an ePCT with a longer timeline is considered, this assumption will have to be revisited. A brief assessment of self-compassion and mindfulness scales outcomes will be performed using the responses collected from the “research only” section of the questionnaires. These results will help better understand the possible mechanisms between the intervention and clinical outcome for future ePCTs. These items will be removed at the conclusion of the pilot to decrease participant burden. All analysis will be performed in SAS 9.4 and significance determined using a two-sided alpha of 0.05.

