**Intervention Structure and Implementation Protocol:**

MBDC group sessions will be held virtually via web-based video calls. Presence Care certified instructors will facilitate the sessions according to the MBDC protocol. Nine sessions including 8 weekly classes (2 hours each) and a retreat (4 hours) will cover several topics (Table 1). The session taught by the African American instructor may include in-person group meetings in that community church setting.

The core course content for each session will be recorded for individuals who are unable to attend the live session. In this pilot, a phone option for CP participation will also be made available. There is currently a group of MBDC graduate meeting weekly by phone. Many of the CPs participating prefer the phone interaction vs. video call. We will explore whether phone participation increases access for participants with lower socioeconomic status and describe any differences in the intervention fidelity.

Instructors will reach out to CPs that miss class sessions with an email checking in and include a link to the recording. CPs will be asked to watch the session and send the instructor a summary about the content to make up the session. Instructors may withdraw CPs who miss more than 3 sessions. CPs will be mailed one chapter of the MBDC workbook for each class (Appendix 1). The CP workbook is currently available in English for in-person and virtual classes. Presence Care is currently in the process of updating the in-person Spanish MBDC workbook for the virtual class mode. Upon completion of the course, participants will be offered the opportunity to participate in a variety of mindfulness maintenance activities, such as weekly, guided virtual group meetings of MBDC graduates.

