## **5 STUDY INTERVENTIONS**

### **5.1 Interventions, Administration, and Duration**

MBDC group sessions will be held virtually via web-based video calls with a phone option available. Presence Care certified instructors will facilitate the sessions and use the MBDC participant Workbook (Appendix 1). Nine sessions including 8 weekly classes (2 hours each) and a half-day retreat (4 hours) will cover several topics (Table 1).

The core course content for each session will be recorded for individuals who are unable to attend. As taught in the Presence Care certification, instructors will reach out to CPs that miss class sessions with an informal email including a link to the recording. CPs will be asked to watch the session and send the instructor a brief summary about the content in order to make up the session. CPs will be emailed one chapter of the MBDC workbook for each class (Appendix 1). The CP workbook is currently available in English for in-person and virtual classes. Presence Care is currently in the process of updating the in-person Spanish MBDC workbook for the virtual class mode. Upon completion of the course, participants will be offered the opportunity to participate in a variety of mindfulness maintenance activities, such as weekly, guided virtual group meetings of MBDC graduates.

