### **5.4 Adherence Assessment**

Adherence to the intervention is defined as attendance of >75% of classes (or watching video makeup) for at least 6 of 9 sessions.

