#### **Hypotheses and Outcomes**

This pilot study will determine if it is feasible to implement the MBDC program with fidelity for testing in a full-scale ePCT. The primary feasibility progression criteria will be assessed using the previously described measures of feasibility, acceptability, and fidelity. For the progression criteria to be met with no modifications, we will require >75% participants attend (or watch video makeup) for at least 6 of 9 sessions. If that number is between 50% and 75%, we would recommend the study progress, however we will make modifications to increase adherence. We also define progression criteria based on the diversity of recruitment within the pilot. If our participants are not representative of the PWLD population's racial and ethnic demographics within each care system, we will recommend changes to the recruitment strategy to encourage a higher enrollment rate of CPs who represent these populations. If progression criteria are met, secondary feasibility measures including the completeness of the clinical outcomes will be used to help direct data collection approach in future trials.

The efficacy hypothesis is that participation in the MBDC course programming will reduce depressive symptoms and burden while increasing self-compassion and mindfulness in CPs for PLWD. These outcomes will be measured using the following assessments:

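### Table 3 compares make-up and real-time completion on the same denominator to judge make-up fidelity, but the comparison mixes live attendance with make-up uptake and does not measure fidelity

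*Combined protocol and SAP*

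**What the plan says.** Table 3 defines b as the care partners who start the course. The row for d_k reads "Number who complete each module in real-time" and is analysed as d_k/b, under the label of module-specific completion rate. The next row counts make-up completions, e_k, analysed as e_k/b, with the instruction "Compare to $d_k/b$ to assess fidelity of make-up offerings".

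Two sections say who make-ups are for. Section 3 (Intervention Structure and Implementation Protocol): "Instructors will reach out to CPs that miss class sessions with an email checking in and include a link to the recording". Section 5.1: "instructors will reach out to CPs that miss class sessions with an informal email including a link to the recording".

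The Aim 1 text of Section 9.5 has a separate assessment: "The fidelity of the make-up video module offerings as a substitute for in-class participation will be evaluated by comparing course outcomes". It sets care partners who took the whole course live against those who used make-ups.

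Make-ups also count towards the main criterion. Section 9.1 (Hypotheses and Outcomes) says "we will require >75% participants attend (or watch video makeup) for at least 6 of 9 sessions", and Section 5.4 likewise credits the video make-up. Module completion rates are among the primary outcomes in Section 9.4.1.

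**The concern.** The two rates in Table 3 share a denominator but not a population at risk. Every starter can attend live, but only those who missed the live session are offered the make-up. A well-attended module therefore leaves little room for e_k/b to be large, and a low value can mean either that few people needed a make-up or that those who needed one did not use it. The comparison cannot tell these apart, and neither reading concerns the quality of the make-up.

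At stake is a descriptive result within a listed primary outcome. Section 9.5 summarises completion patterns by demographics and site. Where live attendance differs between groups, the comparison could make make-ups seem to work better in one group when only attendance differs. That could misinform a decision about keeping or changing make-ups in the full trial.

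**Working it through.** **Inputs.** b, d_k and e_k as defined in Table 3, and the make-up rule from Sections 3 and 5.1. The plan gives no expected value for live attendance, e_k or uptake, so there is no planned figure to reproduce. All counts below are assumed. b = 120 is borrowed from the sample size in Section 9.2, and the rates do not depend on it. One condition is needed that Table 3 does not state: each care partner counts once per module, as live or as make-up.

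**Bound.** Make-ups then come from the b − d_k absentees. Write uptake as u_k = e_k/(b − d_k). Then

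e_k/b = u_k × (1 − d_k/b) ≤ 1 − d_k/b.

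- 75% live: cap 1 − 0.75 = 25%.
- 90% live: cap 1 − 0.90 = 10%.
- e_k can reach d_k only if d_k ≤ b/2.

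**Same uptake (50%), different live attendance:**

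| d_k | e_k | d_k/b | e_k/b | Gap (points) | e_k/d_k | Uptake | Total |
|---|---|---|---|---|---|---|---|
| 108 | 6 | 90% | 5% | 85 | 0.056 | 50% | 95% |
| 84 | 18 | 70% | 15% | 55 | 0.214 | 50% | 85% |
| 60 | 30 | 50% | 25% | 25 | 0.500 | 50% | 75% |

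Absentees behave identically in all three rows, yet the rate, the gap and the ratio all differ.

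**Reversed order:**

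| d_k | e_k | d_k/b | e_k/b | Gap (points) | e_k/d_k | Uptake | Total |
|---|---|---|---|---|---|---|---|
| 108 | 12 | 90% | 10.0% | 80 | 0.111 | 12/12 = 100% | 120/120 = 100% |
| 60 | 15 | 50% | 12.5% | 37.5 | 0.250 | 15/60 = 25% | 75/120 = 62.5% |

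The second module looks better for make-ups on rate, gap and ratio, although its uptake and its total completion are both far lower.

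**How much is live attendance?** I drew live attendance uniformly from 60–95%, 50–90% or 70–90%, and uptake from 0–100% or 30–100%, and took the squared correlation of each with the contrast.

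- Gap d_k/b − e_k/b: live attendance accounts for 68–92% of the variance and uptake for 7–30%.
- Ratio e_k/d_k: live attendance accounts for about 25–70% and uptake for about 22–66%. Uptake has the larger share in all three settings with uptake from 0–100%. Live attendance has the larger share in all three with uptake from 30–100%.

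So live attendance dominates the gap over these ranges. For the ratio the balance depends on the range assumed.

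**The case against.** The strongest reply has three parts. First, Section 9.5 presents Table 3 as an example, and the course-outcome comparison in the same section is the substantive assessment of make-up fidelity. Second, Table 3 says only to compare; it names no gap, ratio or test. Third, a common denominator is a defensible descriptive choice. The two shares add to total completion, and uptake follows from them as (e_k/b)/(1 − d_k/b), so nothing is lost.

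Much of this stands. The information is all there, the results are descriptive, and the plan does have another route to fidelity. But Table 3 is where the module-level rates are defined, and its one stated use of the pair is to judge fidelity. Neither the example label nor the outcome comparison makes that use valid.

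A reader might infer more than the documents support:

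- *That make-ups look weak wherever live attendance is high, whatever absentees do.* This is false. At 90% live with 100% uptake the gap is 80 points and the ratio 0.11. At 82% live with 0% uptake the gap is 82 points and the ratio 0. The better-attended module looks better on both.
- *That any form of the comparison is mainly live attendance.* This is not shown for the ratio.
- *That the caps need no assumption.* They need one count per care partner per module.

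**Conclusion.** The point holds as a minor correction. Given one count per care partner per module, the Table 3 comparison combines live attendance with make-up uptake. It is forced in favour of live sessions whenever more than half of starters attend live, it can put modules in the wrong order, and it does not measure fidelity of content. The caps follow from that counting assumption alone. The worked counts and variance shares are illustrative.

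Two wider conclusions might be drawn and should not be. The plan does not lack an assessment of make-up fidelity, because Section 9.5 has one based on course outcomes. The go-forward decision is not affected either: the main progression criterion is c/b, which does not use the comparison of e_k/b with d_k/b. The consequence is confined to how module-level feasibility results are described and read.

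**What to change.** In Table 3 and the matching text of Section 9.5:

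- Remove the comparison of e_k/b with d_k/b as a measure of fidelity.
- For each module report make-up uptake e_k/(b − d_k), showing numerator and denominator, and total completion (d_k + e_k)/b.
- Label d_k/b as real-time completion, since adherence credits make-ups as well.
- State that each care partner counts once per module.
- Call uptake uptake. Leave make-up fidelity to the course-outcome comparison, with a note that make-up users are self-selected, so a difference in outcomes need not be due to the format.

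The cost is a few lines of wording and slightly more tabulation. b, d_k and e_k are already planned, so no new data are needed.

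There are two downsides. Uptake is unstable when few miss a session: with 120 starters and 90% live attendance the denominator is 120 − 108 = 12. And b − d_k includes care partners who have left the course, who then count as non-uptake. Section 3 says "Instructors may withdraw CPs who miss more than 3 sessions", so this group may not be empty in later modules. The plan should say that they stay in the denominator.
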